**Medical University of South Carolina
Protocol**

PI Name: [name]

Co-PI: [name]

Study Title: Noninvasive Brain Stimulation to Improve Oromotor Function In Neonates

Once protocol is complete, save it as a Word document. Go back to the IRB application and upload the protocol.

TABLE OF CONTENTS – *Prepare a table of contents based on the following outline, including page numbers, and insert here.*

Specific Aims.....	2
Background and Significance.....	2
Preliminary Studies.....	3
Research Design and Study Methods.....	4
Protection of Human Subjects.....	8
References.....	15
Facilities.....	18

A. SPECIFIC AIMS

Preterm infants and term infants who suffer hypoxic ischemic encephalopathy (HIE) are at high risk for motor problems, which primarily manifest as feeding delays during their neonatal hospital admission. Oromotor dyscoordination is very common in both groups of infants, and typically takes 3-6 weeks of working on oral feedings in the hospital before the infant may take enough breast milk or formula to sustain adequate growth for discharge. Occupational therapy usually works with infants once a day to ensure that the feeding particulars, such as nipple choice, frequency of oral feeding, do not tax infant physiology too greatly and to guide learning this motor skill. Feeding difficulty is the primary reason for delayed discharge of preterm or HIE infants. Many of these infants will not be able to master this motor skill before term age (40-42 weeks gestation) and will receive a gastrostomy tube (G-tube) for direct gastric feeding, in order that they may finally be discharged from the hospital to home. Over the past 5 years in our MUSC NICU (2012-2016), we have placed an average of 40 G-tubes per year. This procedure requires general anesthesia for both insertion and eventual take down, and leaves scars in the epigastric area. The G-tube also reinforces the parental perception that their child is not normal and that he or she has a more limited developmental potential than a 'normal' child.

Even with significant brain injury, we know that neuroplasticity in infants may lead to improved, and even near normal outcomes. This neuroplasticity involves stimulating neurogenesis and reparative inter-neuronal connections to improve motor skills in neonatal animal models and in adults after stroke. In addition, we know that rehabilitative training may be enhanced by brain stimulation using a variety of modalities.

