Feeding in neonates involves a sequence of sucking, swallowing, and breathing that requires coordination of the face, head, and neck muscles with the myelinated vagal regulation of the bronchi and the heart (11). In preterm neonates, the muscles needed to feed are underdeveloped, resulting in the need for OT rehabilitation to 'learn' feeding patterns. Preterm neonates' inability to feed effectively is the primary reason for prolonged hospital stays (12). In neonates with HIE, development of cortex and basal ganglia is interrupted, and depending on the severity, normal developmental plasticity is hindered, further contributing to their inability to feed (13). Both types of feeding difficulties involve complex motor learning, which requires integration of sensory and motor pathways. Treating oromotor difficulties during the learned task of feeding with noninvasive brain stimulation that promotes plasticity, poses a highly novel application of taVNS. Our major premise is that in babies at high risk for motor problems, simultaneously delivered brain stimulation via taVNS will boost motor cortical plasticity involved in a learned feeding task, leading to better feeding.

This protocol has 2 specific aims that will be investigated:

Specific Aim 1: Improved Motor Learning - We aim to investigate whether pairing taVNS with rehabilitation training of feeding behavior in preterm and HIE neonates will enhance and accelerate the learning of effective feeding behavior in a dose responsive manner. We call this treatment "taVNS-paired feeding." The primary outcome measures of taVNS-paired feeding will be daily oral milk feeding volume changes from before to during treatment, and number of infants reaching full oral feeds

between once and twice daily taVNS-paired feeding, duration to full feeds, as well as general motor functional impairment as measured by [name] Test of Early infant motor Performance (STEP). Our hypothesis is that taVNS-paired feeding for preterm neonates is feasible, safe and effective at reducing length of stay solely for feeding reasons, compared to historical controls. As part of our safety investigations with separate funding, we may perform taVNS during a clinical modified barium swallow study with pediatric speech language pathologists performing the study and compare 10 swallows with stimulation on and off to determine if taVNS affects swallowing parameters.

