Up to 40 preterm/HIE neonates will be enrolled in this prospective, open-label safety and feasibility trial, with a dose response. The experimental paradigm consists of 2 to 3 weeks of once or twice daily taVNS-paired feeding.

Our control group was investigated by Drs. [name] and [name] at MUSC, who have researched all infants failing feeding and getting Gastrostomy tubes in our nurseries over the past 5 years. We can compare our data to this historical group at our own institution.

All consented participants will receive the active stimulation condition.

taVNS Stimulation (in Detail)

After obtaining consent and describing this procedure to the parents and all members of the baby's care team, we will first, with a 500 μ s, 25Hz pulse, gradually increase the intensity of the TENS unit until the baby can first feel something in their ear. We will use the facial expression change and fidgety movements to determine when the infants feel the stimulation. This intensity will be recorded as the perceptual sensory threshold. The stimulation intensity we will use for this study on taVNS-paired feeding is a small decrement from the perceptual sensory threshold for each infant (-0.1mA), a point at which they should not react to the stimulation. We will retest the sensory threshold before every session.

Determination of Perceptual Threshold

1. Electrode clip will be placed on the left tragus in an enrolled infant at rest. Starting at 0.2mA at 25Hz, we will deliver 5 seconds of pulses, and increase by 0.1mA until the perceptual threshold is achieved by observation of the infant's facial expression, fidgety movements, or NIPPS score. This will be termed the perceptual threshold.
2. We will then deliver this level of microcurrent while the infant is feeding on the first day to determine if the perceptual threshold changes with feeding. Current will then be held constant while pulse width and frequency will be set at 500us and 25Hz, respectively.

3. Finally, we will decrease the microcurrent by 0.1mA *below the perceptual threshold* and administer this taVNS treatment during the feeding and deliver this only while the infant is actively sucking from the bottle.
4. The total duration of this 'on-and-off' taVNS stimulation treatment will continue for 30 minutes or the duration of the feed.
5. We may manually trigger the taVNS stimulation or place a gel EMG electrode over the temporomandibular joint area to trigger the taVNS impulse.

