For safety we will compare HR changes from baseline to during taVNS within subjects. We will compare treatment before and after the taVNS-paired feeding treatment for the rate of feeding volume increase, and days to full po feeds. We will use repeated measures ANOVA to analyze repeated measures such as HR over 5 minutes and mean daily feeding volumes in 7-10 day epochs. We will analyze the number of infants who reach full feeds vs requiring G-tube during taVNS-paired feeding, between once and twice daily stimulation by Chi-squared. We will assess differences in kurtosis parameters from pre-to post taVNS scans by paired t-test, and between those that reach full oral feeds vs those that require a Gtube by unpaired t-test.

Estimated Difficulties, Limitations and Time Frames

Estimated Difficulties. Many of the initial parameters for taVNS in humans, such as frequency and pulse width, were accomplished in trials at MUSC by [name] et al. that were approved by the IRB. In one sense, we will be shrinking many of the components into miniature form to deliver stimulation to neonates and infants. In spite of the clear differences in size and skin between the neonatal and adult ear, the custom electrodes have been fitted to several different weights of infants (2.5-4.0 kg).

Limitations. We will not be delivering a SHAM stimulation paradigm (electrodes and Digitizer with appearance of taVNs treatment without actual current). Our goal is to determine safety and feasibility of active treatment with a dose response in order to investigate whether this should be administered in a larger randomized control trial. In this respect, the comparison we lose in not having a SHAM stimulation is offset by the validation we will receive in the safety and feasibility of active treatment. We will compare our overall results with characteristics of infants who required a Gtube from [name] and [name]'s publications.

Estimated Time Frames. The duration of the study will likely be ~4 years, with 2 years of active enrollment and 18 months of follow-up.

E. PROTECTION OF HUMAN SUBJECTS

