1. RISKS TO THE SUBJECTS

The human subjects involved in this research will be preterm neonates or infants with critical illnesses that preclude oral feeding, such as HIE. Inclusion criteria involves 2 main groups. The first is comprised of typical pre-term, high risk neonates who are in the convalescent near and post-term period and learning to po feed. The second is comprised of neonates that present after severe medical illnesses or brain injury. In both cases, the infants can only be enrolled if they are stable, not making progress with OT training, and are in discussion for Gtube placement. Participants will be excluded if they have major unrepairs congenital abnormalities that limit volume of feeds, cardiomyopathy, significant autonomic instability, such as repetitive, unresolved bradycardia or apnea, or use a continuous positive airway pressure (CPAP) device or other form of high respiratory support preventing them from breathing without assistance.

Targeted/Planned Enrollment Table

Total Planned Enrollment: 40 babies (active)

TARGETED/PLANNED ENROLLMENT: Number of Subjects receiving active taVNS			
Ethnic Category	Sex/Gender		
	Females	Males	Total
Hispanic or Latino	4	5	9
Not Hispanic or Latino	15	16	31
Ethnic Category: Total of All Subjects*			

Racial Categories			
American Indian/Alaska Native			
Asian			
Native Hawaiian or Other Pacific Islander			
Black or African American	8	7	15
White	12	13	25
Racial Categories: Total of All Subjects*	20	20	40

*The “Ethnic Category: Total of All Subjects” must be equal to the “Racial Categories: Total of All Subjects”.

Volunteers of all ethnicities and racial categories will be accepted into this study protocol. No preference will be given based on race, gender or ethnicity. No vulnerable populations or special classes of subjects will be considered for participation.

b. Sources of Materials

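### The primary volume outcome is a change from before to during treatment in Specific Aim 1, but Data Analysis compares a rate before and after treatment, plus epoch means not tied to treatment start

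*Combined protocol and SAP*

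**What the plan says.** Section A, Specific Aim 1: "The primary outcome measures of taVNS-paired feeding will be daily oral milk feeding volume changes from before to during treatment". The number of infants reaching full oral feeds is named alongside it.

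Section D, Data Analysis, gives two volume analyses:

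- A rate: "We will compare treatment before and after the taVNS-paired feeding treatment for the rate of feeding volume increase". The same sentence applies the before-and-after comparison to days to full oral feeds.
- A level, by repeated measures ANOVA: "mean daily feeding volumes in 7-10 day epochs". The epochs are not assigned to time before, during or after treatment.

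The section then analyses "the number of infants who reach full feeds vs requiring G-tube during taVNS-paired feeding" between once and twice daily stimulation.

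Three other places bear on the point. Study Design: "The experimental paradigm consists of 2 to 3 weeks of once or twice daily taVNS-paired feeding". Section E, Risks to the Subjects, describes entrants as "not making progress with OT training, and are in discussion for Gtube placement". Section A says that these infants typically need 3-6 weeks of work on oral feeding in hospital "before the infant may take enough breast milk or formula to sustain adequate growth for discharge".

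The documents do not say how the rate is calculated, when the *after* window begins and ends, or which volume analysis carries the primary outcome.

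**The concern.** A primary outcome should have one quantity and one pair of windows. Here Aim 1 gives a change in volume, before versus during. Data Analysis gives a rate of increase, before versus after, and then a set of epoch means without an anchor. With up to 40 infants, open label and all on active stimulation, the within-infant volume contrast is one of the main signals of efficacy. Several versions without an order of priority leave the choice open until the data have been seen.

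The literal wording of the rate comparison raises a second, conditional problem. Oral intake has a ceiling at full feeds. If the second window opens once the course is over, an infant who reached full feeds during it has little room to increase, and may no longer be in hospital. The rate contrast would then be least informative for the infants who did best.

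**Working it through.** **Side by side.** The plan gives no sample size, power or effect-size calculation for volume, so there is no figure of its own to reproduce.

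| Place | Quantity | Windows |
|---|---|---|
| Specific Aim 1 | change in daily oral volume | before, during |
| Data Analysis, rate | rate of volume increase | before, after |
| Data Analysis, epochs | mean daily volume | 7-10 day blocks, no anchor |

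The missing anchor matters because the course lasts 2 to 3 weeks. A 14-day course holds 14/7 = 2 epochs of 7 days but 14/10 = 1.4 epochs of 10 days; a 21-day course holds 3 or 2.1. Unless epochs are counted from the first session and given one length, an epoch can mix treated and untreated days.

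**Illustration of the literal reading.** All inputs are assumed except the course length: intake is flat at 40% of full feeds before treatment, rises linearly to 100% by day d = 7, 10 or 14 of a 14-day course, and then stays at 100%.

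- Least-squares slope on days 0-14 (sum of squares of day about its mean = 280): 1200/280 = 4.29 for d = 7, 1320/280 = 4.71 for d = 10, and 60/14 = 4.29 for d = 14, in percentage points per day.
- Mean level on days 1-14: 1220/14 = 87.1%, 1130/14 = 80.7% and 1010/14 = 72.1%, against 40% before.
- Slope on days 14-21: 0 in all three cases. The slope before treatment is also 0, so the before/after rate contrast is 0.

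**Wider range.** With a start at 20-60% of full feeds, a 14- or 21-day course, and full feeds at day 7 or on the last day, the average rate over the course is (100 - start)/course length. This runs from 40/21 = 1.9 to 80/14 = 5.7 points per day. Treating the rise as continuous, the mean level during treatment is 60% to 93%. The rate after full feeds is 0 throughout.

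**In mL.** Assume full intake of 120-160 mL/kg/day and a gain of 20-30 g/day; weights of 2.5-4.0 kg are the range given for electrode fitting. The rate after the course, from growth alone, is gain × intake: 0.02 × 120 = 2.4 to 0.03 × 160 = 4.8 mL/day. The rate during a 14-day course starting at 40% is [intake × (weight + 14 × gain) - 0.4 × intake × weight]/14, which gives 15.3 to 32.2 mL/day. On this scale the later rate is small but not zero.

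**Ordering.** An assumed partial responder who rises from 40% to 70% over 14 days and continues at the same pace has a slope after the course of 30/14 = 2.1 points per day. On the literal rate contrast this infant ranks above every complete responder.

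**Why a rate should stop at full feeds.** The whole-course slope is 4.29 both for full feeds at day 7 and for full feeds at day 14, so plateau days hide a twofold difference in speed. Ending the calculation at full feeds gives 60/7 = 8.6, 60/10 = 6.0 and 60/14 = 4.3.

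**Other reading.** If *after* means after the first session, the second window is the course itself. The rate is then positive and the ceiling problem largely goes away.

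**The case against.** The strongest reply is that *after* is loose wording for after treatment starts. The same sentence applies it to days to full oral feeds, and an infant who reached full feeds during the course has no such days left once it is over. A count from treatment onset makes better sense of that half. No section describes a volume window after the course. Aim 1's phrase about volume changes could itself be taken as a rate. On this view the two sections mean nearly the same thing.

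That is a fair reading, but it does not settle the matter. Data Analysis writes *during* for heart rate in the preceding sentence and for the full-feeds comparison, so a different word naturally suggests a different window. If *during* was meant, the same edit is needed.

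A reader might go further and infer that the plan scores complete responders as zero, is biased against them, and could turn the Aim 1 conclusion on this choice. The documents do not support that:

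- No passage states a zero score. It requires a window after the course ends and volumes still recorded then. Since adequate oral intake is tied to discharge, the value may be missing instead.
- Flat intake before treatment comes from the narrative in Risks to the Subjects. The inclusion criteria ask for discussion of a G-tube for poor feeding and 30 or 14 days of working on oral feeding, not for a flat trend.
- Data Analysis also covers epoch mean volumes and the number reaching full feeds. Both would register a responder.
- The end of Section B places the feeding hypotheses second to safety and feasibility.

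**Conclusion.** The inconsistency stands without any assumption: the primary volume outcome differs in quantity and window between Specific Aim 1 and Data Analysis, and the epoch analysis has no anchor. It should be corrected before the data are analysed.

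The effect on complete responders is conditional. If *after* means after the course ends, intake before treatment is flat and volumes are still recorded, the rate contrast is 0 on the percent-of-full-feeds scale, against 4.3 to 4.7 points per day during the course in the main example. In mL it is about 2.4 to 4.8 per day after the course, against about 15 to 32 during it. If such infants have gone home, the contrast is missing. If *after* means after treatment starts, the bias largely disappears and the conflict of wording remains. The claim that this alone would decide Aim 1 is not supported, because the other planned analyses would still show a complete response.

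**What to change.** In Data Analysis:

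1. Replace before-and-after with before-and-during for the volume comparison, to match Specific Aim 1.
2. Name one primary volume measure: the change in mean daily oral volume from a fixed pre-treatment epoch to epochs counted from the first taVNS session. State one epoch length within the 7-10 day range; 7 days divides both a 14-day and a 21-day course evenly.
3. If a rate is also reported, label it secondary and compute it from the first session to the earlier of full oral feeds and end of course, so that plateau days are excluded.

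Specific Aim 1 can keep its window; it needs only the words mean daily volume by epoch if exact agreement is wanted. The same daily volumes serve, with no new data. The only cost is that the post-course rate comparison is dropped.

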Specific Aim 2: Brain Changes - We aim to determine if white matter fiber tracts show improved integrity as measured by diffusion imaging (DKI) before, after a 2-week treatment taVNS-paired feeding course, and whether treatment improves neuronal energetics in the basal ganglia as measured by magnetic resonance spectroscopy (MRS). Unsedated MRS and DKI imaging will last approximately 40 minutes, and will be done before and after the two-week taVNS-paired rehab treatment session. The changes in white matter tract diffusion parameters and N-acetylaspartate (NAA) and glutathione (GSH) concentration in the basal ganglia and thalamus will be compared with published changes of these parameters over gestational age in preterm infants (14, 15) and with our own MRS data in preterm and HIE infants who did not receive taVNS.

We will perform DKI to determine the effects of taVNS on plasticity, and to identify areas of the brain involved in afferent vagal activation. We propose utilizing the concurrent taVNS/fMRI method developed by [name] at MUSC to determine whether taVNS activates the CNS and afferent vagal network in a subset of preterm and term infants in the study.

B. BACKGROUND AND SIGNIFICANCE

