3. POTENTIAL BENEFITS OF THE PROPOSED RESEARCH TO THE SUBJECTS AND OTHERS

taVNS paired with oromotor feeding training may enhance feeding skills, and enable the infants to learn this task more quickly and be discharged from hospital sooner. The treatment could potentially help avoid placement of a G-tube, but we will not be able to determine this from this dose-finding study. The treatment may also help with development of other motor skills, which we will assess by neurodevelopmental tests. We may also discover that taVNS-paired feed improves swallowing function, but even if we do not show any change in swallowing function, this data will support the safety of taVNS in neonates and infants. However, there may be no direct benefit to the participant, but we will gain knowledge about taVNS in infants, and strategies to improve oromotor skill training.

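### Repeated-measures ANOVA on feeding volumes may describe a subset of infants selected by outcome, in a direction the documents do not determine

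*Combined protocol and SAP*

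**What the plan says.** Specific Aim 1 lists, among the primary outcome measures, "daily oral milk feeding volume changes from before to during treatment". The analysis is given in one sentence of section D, Data Analysis: "We will use repeated measures ANOVA to analyze repeated measures such as HR over 5 minutes and mean daily feeding volumes", the volumes being "mean daily feeding volumes in 7-10 day epochs".

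Section D, Study Design, sets the size and the course: "Up to 40 preterm/HIE neonates will be enrolled in this prospective, open-label safety and feasibility trial, with a dose response" and "The experimental paradigm consists of 2 to 3 weeks of once or twice daily taVNS-paired feeding". Specific Aim 2 describes imaging "after a 2-week treatment taVNS-paired feeding course", so the course length is stated in two ways.

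On leaving the series through success, section A says "Feeding difficulty is the primary reason for delayed discharge of preterm or HIE infants", and section E.3 hopes that treatment will "enable the infants to learn this task more quickly and be discharged from hospital sooner". On leaving through failure, the inclusion criteria admit only infants for whom a G-tube is already under discussion. Data Analysis counts both end states, full feeds and G-tube, during the treatment period.

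The text available does not state the number of epochs, whether a partly observed epoch counts, whether volumes are recorded after full feeds, discharge or G-tube, or what value an infant takes after exit.

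**The concern.** Classical repeated-measures ANOVA needs a complete row per infant. Where rows are incomplete and no other rule is given, the usual result is that those infants drop out of the analysis. That does little harm when values are missing by accident. Here the outcome itself may cause the gap: a fast learner may be discharged before the last epoch ends, and an infant making no progress may go to surgery.

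Losing fast learners pulls the estimated gain down, and losing failures pushes it up. If exit rates differ between once-daily and twice-daily treatment, the error could also differ between the two and distort the dose comparison. With at most 40 infants, the number left could be small. Because epoch length and the partial-epoch rule are open in an open-label study, both could be chosen after the data have been seen.

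**Working it through.** The plan states no effect size, SD, dropout rate or exit rate, so there is no figure of its own to reproduce.

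**Step 1. Whole epochs per course** = floor(course days / epoch days), from Study Design and Data Analysis.

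| Course | 7-day epochs | 10-day epochs |
|---|---|---|
| 14 days | 2 | 1 |
| 21 days | 3 | 2 |

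With one to three epochs, an exit in week 2 or 3 can remove the last one.

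**Step 2. Infants left in a complete-row analysis** = 40 × (1 − share leaving before the last epoch ends). Shares of 10, 20, 30, 40 and 50% leave 36, 32, 28, 24 and 20 infants. The documents do not give the share.

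**Step 3. Illustration of the error.** Every input in this step is an assumption, apart from the course and epoch lengths.
- Volume is a percentage of full intake: baseline 40 (SD 12), then a straight line per infant with mean slope 1.5 to 2.4 points per day (SD 1.5).
- Infants leave through success at 95%.
- Of infants with slope below 0.5, 50 to 100% leave for G-tube from day 10, on days spread evenly.
- Gain = mean volume in the last whole epoch − baseline.
- Error = (gain in infants kept) / (gain in all infants, had all been followed) − 1.

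| Scenario | Epoch counts if | Kept | Gain, kept | Gain, all | Error |
|---|---|---|---|---|---|
| Slope 2.4, 21 days, 7-day epochs, half of low-slope infants leave | fully observed | 54% | 29.2 | 37.7 | 29.2/37.7 − 1 = −23% |
| Slope 1.5, 14 days, 7-day epochs, all low-slope infants leave | fully observed | 74% | 20.0 | 16.3 | 20.0/16.3 − 1 = +23% |
| Slope 1.5, 14 days, one 10-day epoch | fully observed | 99% | 8.1 | 8.2 | 8.1/8.2 − 1 = −1% |

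Of 40 infants, 54% is about 22 (40 × 0.54 = 21.6) and 74% is about 30 (40 × 0.74 = 29.6).

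If any observed day makes an epoch count, the first error falls to about −8% and the second to about −1%. Over the scenarios run on these inputs, the range under that rule is about −8% to +5%.

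**Step 4. Dependence on the assumptions.** A second, more dispersed set of inputs used slope SD 3, discharge two days after full volume, and G-tube at day 14 for infants less than 10 points above baseline. With a 21-day course, 7-day epochs and mean slope 2:
- Only successes leave, whole epochs required: 10.4 against 25.9, or −60%.
- Failures also leave, whole epochs required: 37.4 against 26.0, or +44%.
- Failures also leave, any observed day counts: 44.7 against 26.0, or +72%.
- Volumes recorded to the end for everyone: 26.0 against 26.0, no error.

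With mean slope 4 the two kinds of exit nearly offset under the whole-epoch rule: 40.4 against 43.8, or −8%. The percentages in Step 3 are therefore illustrations, not bounds.

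**Step 5. Does a mixed model suffice alone?** No. Fitted to the available values only, a linear mixed model overshot by up to about 13%, because it extrapolates successes past the full-feeds ceiling.

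**The case against.** The strongest reply is that the plan never says incomplete infants are dropped. The unit is an epoch mean, and an infant seen for three days of an epoch still has a mean. The primary measure is a change from before to during treatment, and every treated infant has days in both periods. On that reading nobody need be lost, although unequal observation time would still affect the size of the change. Both exits also appear elsewhere: Data Analysis plans days to full feeds, the rate of volume increase, and full feeds versus G-tube by dose. And this is a pilot of up to 40 infants.

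Much of this stands. Deletion is the usual behaviour of the method, not a stated rule, and the size of the error depends heavily on the epoch definition. But the plan does not adopt the lenient reading either, and Step 4 shows that counting partial epochs is not always enough on a 21-day course. Days to full feeds and the count of end states keep both groups in view, but neither estimates volume change, which is a primary measure in its own right.

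**Conclusion.** The point holds as a risk of selection in one primary analysis, in an unknown direction. Under the first set of assumed inputs the error in last-epoch gain is about −23% to +23% when epochs must be complete. It is about −8% to +5%, often near zero, when partial epochs count or the course holds one 10-day epoch. More dispersed inputs give larger errors. All of these figures rest on assumed baselines, slopes and exit times, and on last-epoch gain as the target, which the protocol does not name.

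A reader might infer that the estimate describes only infants who neither succeed nor fail. The documents do not support that: infants who reach either end state late in the course or after it stay in, and no exit times are given. A reader might also infer that the trial loses its successes. That applies at most to the volume analysis, because the companion analyses count them.

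**What to change.** Change section D, Data Analysis, for feeding volumes; this point does not touch the heart-rate analysis.

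1. Replace the repeated-measures ANOVA with a linear mixed model on all available daily values, with random intercept and slope per infant. Express volume as a fraction of full intake and state the denominator.
2. Fix the epoch length, the number of epochs and the rule for partly observed epochs before analysis. The two statements of course length must be reconciled, since they determine how many epochs exist.
3. Treat infants discharged on full oral feeds as at full intake for their remaining scheduled days. Without this the linear model overshoots the ceiling.
4. Use G-tube infants' data up to surgery. State the value assumed afterwards and vary it in a sensitivity analysis, for example last oral fraction carried forward against available data only.
5. Report how many infants contribute to each epoch and the reason for each exit, by once-daily and twice-daily treatment.

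The cost is analysis wording and a record of exit dates and reasons. The downside is that values after exit are assumptions. Filling them in as if observed understates uncertainty, so the results should be shown with and without them.
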